6.3.1 Participant numbering

Each participant is uniquely identified in the study by a Participant Number (Participant No.) assigned by Novartis when the participant is first enrolled for screening and is retained as the primary identifier for the participant throughout his/her entire participation in the trial.

The participant number, assigned by Novartis, is composed of a Site Number (Site No.) and a sequential participant number suffixed to it, so that each participant is numbered uniquely across the entire database. Once assigned to a participant, the participant number will not be reused.

Upon signing the informed consent form, the participant is assigned the next sequential number available in electronic data capture (EDC) system. The investigator or his/her staff will contact the IRT and provide the requested identifying information for the participant to register them into the IRT. The site must select the case report form (CRF) book with a matching Participant Number in the EDC system to enter data.

If a participant fails screening and rescreens for the study, THEN the participant must sign a new ICF and be issued a new participant number prior to any screening assessment being conducted for the participant under the new screening participant number. If the participant fails to be treated for any reason, the IRT must be notified within 2 days that the participant was not treated. The reason for not being treated will be entered on the appropriate CRF.

6.3.2 Treatment assignment, randomization

The randomization numbers will be generated using the following procedure to ensure that treatment assignment is unbiased and concealed from participants and investigator staff. A participant randomization list will be produced by the IRT provider using a validated system that automates the random assignment of treatment arms to randomization numbers. These randomization numbers are linked to the different treatment arms.

At Baseline visit, all eligible participants will be randomized via Interactive Response Technology (IRT) to one of the treatment arms. The investigator or his/her delegate will contact the IRT after confirming that the participants fulfills all the inclusion/exclusion criteria. The IRT will assign a randomization number to the participant, which will be used to link the participants to a treatment arm and will specify a unique medication number for the first package of study drug to be dispensed to the participant. The randomization number will not be communicated to the caller.

Japanese participants will be assigned to treatment arms with randomization blocking for Japan that is separate from the randomization for all other countries.

These randomization numbers are linked to the different treatment arms, which in turn are linked to medication numbers. A separate medication list will be produced by or under the responsibility of Novartis Drug Supply Management using a validated system that automates the random assignment of medication numbers to packs containing the investigational drug(s).

This will allow a balanced assignment of participants to each treatment arm.

The randomization scheme for participants will be reviewed and approved by a member of the Randomization Group.

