6.3.3 Stratification

There will be no stratification for Japanese participants. They will be included in a separate randomization list as described in Section 6.3.2.

To ensure balance of participants among the 4 treatment groups, the following stratum levels will be implemented:

- T2DM yes
- T2DM no

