Combination vs. placebo (test 1, k = 1, i = Cmb, j = Plc)

Tropifexor (LJN452) vs. placebo (test 2, k = 2, i = LJN, j = Plc); licogliflozin (LIK066) vs. placebo (test3, k = 3, i = LIK, j = Plc)

Combination vs. tropifexor (LJN452) (test 4, k = 4, i = Cmb, j = LJN); combination vs. licogliflozin (LIK066) (test 5, k = 5, i = Cmb, j = LIK)

There are ten potential tests to be performed for the two primary endpoints (five for each primary endpoint), and it is important to control the overall Type I error rate for these tests. The alpha recycling graph presented in Figure 12-1 shows how alpha transfers among them. If the data fails to reject the null hypothesis of a test, then the alpha of that test will not be passed to others. This restriction ensures the control of overall Type I error rate. Again, for the primary

Confidential

Amended Protocol Version 02 (Clean) Protocol No. CLJN452D12201C endpoints, the overall alpha is set at two-sided 5%. A logistic regression model with the logit of probability for histological response as the dependent variable, treatment groups as the main effect, baseline fibrosis stage and T2DM (No/Yes) as explanatory variables, and the baseline BMI as a covariate will be utilized to test the hypotheses at each step. While this model will be the typical logistic regression in most cases, it should be set as the Firth logistic regression if some arm (such as the placebo) has a low response rate, as the Firth method returns less biased results for data with rare events. The null hypothesis of *k*th test, if executed, will be rejected if the p-value for the coefficient of treatment effect in the *k*th comparison is less than or equals to its corresponding alpha. If no alpha is passed to a specific comparison, then its corresponding test will not be performed and p-value will not be calculated. More statistical specifications of the model will be described in the statistical analysis plan (SAP).

The number and percentages of histological responders at week 48 in FAS will be summarized by treatment groups. The difference between the treatment of interest and the alternative treatment will be presented along with 95% confidence interval calculated based on the normal approximation for distribution of the difference between two binomial random variables.

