# 2.2.1 Subgroup of interest

Exploratory analysis on the primary endpoint (Section 2.13.1) will be performed on following subset of FAS.

[figure not shown]
- FAS with baseline fibrosis stage of F2
- FAS with baseline fibrosis stage of F3
- FAS with T2DM at baseline
- FAS without T2DM at baseline
- FAS asian (Based on race collected on the Demographics CRF page)
- FAS non-asian (Based on race collected on the Demographic CRF page)

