With the sample data collected in the study, the naive differences  $P_1-P_{2i}$  can be estimated using  $p_1-p_{2i}$  with unpooled standard error SE = sqrt(  $p_1*(1-p_1)/n_1 + p_{2i}*(1-p_{2i})/n_{2i}$ ).

The hierarchical testing procedure based on odds ratio can be formulated as one-sided statistical tests ( $\alpha$ =0.05) for

H0i: 
$$\frac{P1(1-P2_i)}{P2(1-P1_i)} \le 1$$
 vs. H1i:  $\frac{P1(1-P2_i)}{P2(1-P1_i)} \ge 1$ 

executed sequentially for i=(1, 2), where H02 is tested only if H01 is rejected.

A logistic regression model with the logit of probability for histological response as the dependent variable, treatment groups as the main effect, baseline fibrosis stage (2 vs. 3) and T2DM (No/Yes) status as co-factors, and baseline BMI as a covariate will be utilized to test the hypothesis at each step of the hierarchical testing procedure.

The choice of co-factors/covariates, the considerations for their collinearity, potential interactions with treatment effect and model specifications are further discussed in Section 5.4.1.

The logistic regression analyses can be implemented in SAS LOGISTIC procedure with the *scale=williams* and *firth* options in the model statement, executed together with the multiple imputation (MI) methods outlined in Section 2.5.3.

Odds ratios and 95% CI of the probabilities of histologic response between study treatments can be back calculated as the exponentiation of the corresponding coefficients estimated from the logistic regression.

One logistic regression model can be fitted on all FAS data from the three treatment arms to estimate the pairwise odds ratios and associated p-values.

Given placebo effects (Table 3-1) reported in the published literature and with Firth correction, a model convergence issue is not expected. In the case a convergence issue occurs and cannot be resolved with other appropriate technical approaches, a reduced model may be used for the primary analysis. The reduced model will be determined by removing baseline BMI, fibrosis stage and T2DM status sequentially from the full model until the convergence issue is resolved. If a reduced model has to be used, impacts on the interpretation of primary analysis results will be discussed in the core CSR in combination with results from sensitivity analysis.

Existence of extremely influential baseline BMI values will be examined with Cook's distance plot based on complete cases before MI.

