#### 5.4 Statistical models

#### 5.4.1 Logistic regression model for primary and key secondary analysis

Hierarchical testing procedure and the hypothesis tests at each step for primary and key secondary analyses are defined in Section 2.5 and Section 2.6.

For binary dependent variable and considering the link of NASH with many metabolic risk factors, a logistic regression model is used to allow more flexibility in adjusting for both categorical and continuous explanatory variables.

The efficacy of LIK066 for NASH is postulated due to its ability to improve obesity and diabetes. Frequently regarded as two manifestations of metabolic syndrome, T2DM and NAFLD commonly exist together with, for example, insulin resistance as one of the key pathological factors. The randomization of this study is stratified by patient's T2DM status at baseline. Links between obesity and histologic NASH were also well known (Lassailly et al 2015, Vilar-Gomez et al 2015).

improvement					
Study	Intervention	population	Histologic endpoint	effect	
Vilar-Gomez	Weight loss	Obese w.	Resolution of NASH	p <0.01ª	
et al 2015	by life style change	NASH	Fibrosis status	p<0.00ª	
Lassailly et al	Bariatric	Obese w.	NASH resolution	85%	
2015	surgery for	NASH	Fibrosis improvement	p<0.0001 b	
	weight loss		Ballooning	p<0.0001 b	

**Table 5-4**Association of weight loss with NASH resolution or liver fibrosisimprovement

a: p-value based on Cochran-Mantel-Haenszel  $\chi^2$  trend test between weight loss categories and the histologic endpoint stratified by age older than 55 years, sex, type 2 diabetes, BMI>=35

Lobular inflammation

p<0.0001b

b: p-value based on Wilcoxon signed rank test for paired data before and 1 year after bariatric surgery

Hence BMI and T2DM status are anticipated to be prognostic of histologic changes, with or without therapeutic intervention, and will be included in the logistic regression model as confounding factors.

Novartis	For business use only	Page 42
SAP		CLJN452D12201C

LJN452 is anticipated to improve liver fibrosis, with or without NASH resolution, based on previous studies of other FXR modulators (Neuschwander Tetri et al 2015, Younossi 2019). The baseline stage of fibrosis is a plausible prognostic factor for histologic response, especially for the fibrosis improvement itself, and included also as a factor in the logistic regression model.

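### Japan is randomised from its own separately blocked list but has no term in the primary and key secondary models; the cost is a little power, not validity.

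*Protocol*

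**What the plan says.** Protocol Section 6.3.2: "Japanese participants will be assigned to treatment arms with randomization blocking for Japan that is separate from the randomization for all other countries".

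Protocol Section 6.3.3: "There will be no stratification for Japanese participants. They will be included in a separate randomization list as described in Section 6.3.2". It then names T2DM yes and T2DM no as the only stratum levels. SAP Section 5.4.1 agrees: "The randomization of this study is stratified by patient's T2DM status at baseline".

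The primary model in Protocol Section 12.4.2 has treatment plus "baseline fibrosis stage and T2DM (No/Yes) as explanatory variables, and the baseline BMI as a covariate will be utilized to test the hypotheses". SAP Section 2.5.2 has the same terms, with baseline fibrosis stage and "T2DM (No/Yes) status as co-factors, and baseline BMI as a covariate will be utilized to test the hypothesis at each step". The key secondary endpoint uses the same method (Protocol Table 12-1; SAP Section 2.6.2). The supportive CMH analysis (SAP Sections 2.5.4 and 5.4.4) stratifies by fibrosis stage, T2DM and BMI.

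None of these has a term for Japan, country or region, and no reason is given. The nearest items are region as a summarised baseline characteristic (SAP Section 2.3) and an exploratory subgroup, "FAS asian (Based on race collected on the Demographics CRF page"). The second is defined by race, not by randomisation list.

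The SAP supplied is dated December 2019 and describes three arms and 210 patients. It says it may be amended after a protocol amendment.

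**The concern.** When a group is randomised in its own blocks, arm sizes are balanced within that group by design. A model that omits the group computes its variance as if chance imbalance on it were still possible. If the group is prognostic, the reported uncertainty is then larger than the true sampling variability, so the test rejects less often than its nominal level and loses power. T2DM, the declared stratum, is in the model. Japan restricts the randomisation in the same way and is not.

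What is at stake is efficiency. Table 12-4 shows power for combination versus placebo on endpoint A (fibrosis improvement without worsening of NASH) of only 0.55 at 95 per arm, so a few points that need no extra participants are worth having.

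**Working it through.** **1. The plan's own power figure.** Inputs: response rates 35% vs 20% (endpoint A) and 25% vs 10% (endpoint B), correlation +0.5, and 140 vs 80 participants (Protocol Section 12.8.1). The two-sided 5% alpha is split evenly, so each endpoint is tested at 0.025, critical value 2.241 (Section 12.4.2). For an unpooled z-test:

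- Endpoint A: SE = √(0.35×0.65/140 + 0.20×0.80/80) = 0.0602; power ≈ Φ(0.15/0.0602 − 2.241) = 0.60.
- Endpoint B: SE = √(0.25×0.75/140 + 0.10×0.90/80) = 0.0496; power ≈ Φ(0.15/0.0496 − 2.241) = 0.78.
- At least one endpoint, 200,000 simulated trials: 0.849 (stated 0.85). At 95 per arm: 0.800 (stated 0.80).

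The stated power reproduces. It comes from a test with no covariates, so it does not depend on a Japan term.

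**2. What the randomisation cells are.** Section 6.3.3 can be read in two ways. If Japan is merely not labelled a stratum, its list may also be split by T2DM. If the Japanese list is not split by T2DM, the cells are Japan, elsewhere with T2DM, and elsewhere without T2DM. On both readings Japan is a randomisation group that the model leaves out.

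**3. Effect of the missing term.** The documents give no Japanese share, block size or prognostic effect. Assumed: share 5%, 10% or 20% of 380 (19, 38 or 76 participants); response odds ratio for Japan 1, 2 or 3; separate 7:4:4:4 blocks of 19 for Japan and for the rest (7:4:4:4 = 1.75:1:1:1). The test is a logistic Wald test of combination vs placebo on endpoint A at 0.025, with up to 10,000 trials per setting under the null (20% vs 20%) and up to 6,000 under the alternative (35% vs 20%).

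| Share | Japan OR | Type I error, without → with Japan | Power, without → with Japan | Gain (points) |
|---|---|---|---|---|
| 5% | 1 | 0.0219 → 0.0219 | 0.5386 → 0.5413 | 0.3 |
| 5% | 2 | 0.0216 → 0.0228 | 0.5173 → 0.5300 | 1.3 |
| 5% | 3 | 0.0199 → 0.0208 | 0.5238 → 0.5443 | 2.1 |
| 10% | 1 | 0.0250 → 0.0255 | 0.5304 → 0.5323 | 0.2 |
| 10% | 2 | 0.0213 → 0.0226 | 0.5287 → 0.5445 | 1.6 |
| 10% | 3 | 0.0200 → 0.0216 | 0.5290 → 0.5547 | 2.6 |
| 20% | 1 | 0.0239 → 0.0243 | 0.5220 → 0.5248 | 0.3 |
| 20% | 2 | 0.0227 → 0.0241 | 0.5203 → 0.5420 | 2.2 |
| 20% | 3 | 0.0194 → 0.0225 | 0.5417 → 0.5787 | 3.7 |

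The Monte Carlo standard error of a type I error entry is about √(0.025×0.975/10,000) = 0.0016, so single entries should not be over-read. The pattern is consistent: no inflation, and more conservatism as the Japan effect grows. Trials in which the ordinary fit failed were dropped. In the first null setting that was 10,000 − 9,137 = 863 (8.6%), which is a direct sign of sparseness when Japan is small.

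**4. Why power rises.** In a second simulation with Japan exactly balanced across arms, adding the term did not shrink the model standard error of the log odds ratio. At 10% share and OR 2 the standard error went from 0.332 to 0.334, and the log odds ratio from 0.771 to 0.787. The ratio of estimate to standard error went from 0.771/0.332 = 2.32 to 0.787/0.334 = 2.36. At 20% share and OR 3 the changes were 0.331 to 0.341 and 0.771 to 0.817, with the ratio going from 2.33 to 2.40. The estimate moves away from zero by more than the standard error grows.

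**The case against.** The strongest reply is that the benefit is hypothetical. The documents do not show that Japan is prognostic or say how many participants it will contribute. Japan is one of 28 distinct country entries in SAP Table 2-3, and about 155 centres are planned, so a 20% share is the favourable extreme. If Japan is not prognostic, the gain is about 0.3 points or less. This stands, and it is why the point is minor.

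Three points on cost also stand:

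- The odds ratio is non-collapsible, so adding Japan changes the quantity estimated, and the odds ratio is the summary measure of both primary estimands. The change is small, and the estimate is already conditional on fibrosis stage, T2DM and BMI.
- The SAP's model always uses Firth, but the current protocol uses it only if some arm has a low response rate. Firth cannot be taken as the default.
- SAP Sections 2.5.2 and 2.5.3 fix a drop order for non-convergence and a list of imputation predictors. Both need matching edits.

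A reader might infer more than the documents support. One inference is that the primary test is invalid or its type I error inflated; the simulations show the opposite direction. Another is that adding Japan buys a smaller standard error, or that its share of outcome variance measures the gain. That is linear-model reasoning; step 4 shows why it fails for a logistic odds ratio. A third is that Section 6.3.3 should simply call Japan a stratum, which could erase a statement that the Japanese list is not split by T2DM.

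**Conclusion.** The point holds as a small efficiency loss and an unclear description of the randomisation. Japan is a randomisation group that the primary and key secondary models omit. The omission causes no bias in the test and no type I error inflation, and it leaves the stated 0.85 power unaffected. If Japan is prognostic, the test is mildly conservative and loses about 0 to 4 points of power on endpoint A.

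That size rests on an assumed Japanese share of 5-20%, a response odds ratio of 1 to 3 and blocks of 19. It also rests on complete data and on models without fibrosis stage, T2DM or BMI; if those absorb part of any Japan effect, the gain is smaller. The effect on endpoint B and on the joint success criterion was not simulated.

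**What to change.** 1. Add Japan (yes/no) as a factor in the primary and key secondary logistic models.
2. Add it to the predictors of the multiple-imputation model, so that imputation and analysis stay aligned.
3. Put it first in the drop order for non-convergence, ahead of BMI, fibrosis stage and T2DM.
4. State that the Firth fit will be used if the Japanese stratum is sparse, whatever the response rates by arm.
5. Reword Protocol Section 6.3.3 to say that Japan has its own randomisation list and whether that list is also split by T2DM.

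The cost is one binary term, the matching edits to the imputation and convergence rules, and an odds ratio conditional on one more factor. The SAP must in any case be updated to the four-arm, 380-participant design. The change should be fixed before unblinding.

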6.3.3 Stratification

There will be no stratification for Japanese participants. They will be included in a separate randomization list as described in Section 6.3.2.

To ensure balance of participants among the 4 treatment groups, the following stratum levels will be implemented:

- T2DM yes
- T2DM no

6.4 Treatment blinding

This is a double-blind study: participants, investigator staff, persons performing the assessments, and Novartis clinical trial team (or delegates) will remain blinded to the identity of study treatments from the time of randomization (until final database lock), using the following methods:

- 2. Randomization data will be kept strictly confidential until the time of final database lock and will not be accessible by anyone else involved in the study with the exceptions in Table 6-4.
 - a. The randomization codes will be disclosed to an independent analysis team to prepare safety and efficacy reports for the DMC. The independent analysts will keep randomization data confidential until data base lock. Data will be shared with the study team under blinded conditions.
- 3. The identity of the treatments will be concealed by the use of placebo that are each identical in packaging, labeling, schedule of administration, appearance, taste and odor to the respective active treatment. Placebo capsules/tablet will be given in active treatment groups when needed to maintain blinding as described in Section 6.1.3.

A double-dummy design is used because the identity of the study treatment cannot be disguised, as the drug products are visibly different.

Unblinding will only occur in the case of participant emergencies (see Section 6.6.2) and at the conclusion of the study. Unblinding a single participant's treatment at a site for safety reasons (necessary for participant management) will occur via an emergency system in place at the site. As a result the participant should be discontinued from the study treatment.

At the time of safety review, the DMC will review unblinded reports created by an independent analysis team. More details will be provided in the DMC charter.

Table 6-4Blinding and unblinding plan

Time or Event				
Role	Randomizatio n list generated	Treatment allocation & dosing	Safety event (single participant unblinded)	Safety review
Participants	В	В	В	В
Site staff	В	В	UI	В
Novartis CTT	В	В	UI	В
Global Clinical Supply	UG	В	UI	В
Randomization Office	UI	UI	UI	UI
Unblinded Pharmacovigilance sponsor staff	В	UI	UI	В
Statistician/statistical programmer	В	В	UI	В
Data Monitoring Committee(DMC) and independent statistician/programmer supporting DMC	UI	UI	UI	UI
All other sponsor staff not identified above (i.e. trial team, project team, management & decision boards, support functions)	В	В	В	В

Key:

UG: Unblinded at the group level (i.e has access to unblinded group level summary results, but not to the individual participant treatment codes)

UI: Unblinded to individual participant treatment codes

B: Completely blinded

6.5 Dose escalation and dose modification

6.5.1 Dose escalation guidelines

There is no provision for dose escalation of study medication doses in the protocol

6.5.1.1 Starting dose

Not applicable

6.5.2 Definitions of dose limiting toxicities (DLTs)

Not applicable as this is not a dose ranging study.

6.5.3 Dose modifications

Temporary interruptions of study medication are permitted. Study medication should be reintroduced under careful monitoring if the investigator feels it is in the best interest of the participant.

For participants who do not tolerate the protocol-specified dosing schedule, dose interruption is recommended in order to allow participants to continue the study treatment, based on investigator's discretion.

These dose interruptions must be recorded on the appropriate CRF.

6.5.4 Follow-up for toxicities

Participants whose treatment is interrupted or permanently discontinued due to an adverse event or clinically significant laboratory value, must be followed up at least once a week (or more frequently if required by institutional practices, or if clinically indicated) for 4 weeks, and subsequently at approximately 4 week intervals, until resolution or stabilization of the event, whichever comes first. Appropriate clinical experts such as ophthalmologist, endocrinologist, dermatologist, psychiatrists, etc., should be consulted as deemed necessary. Further guidelines and recommendations for the management of specific study treatment combination-induced toxicities (i.e. renal, liver) are provided in Section 10.2 and Section 16. All participants must be followed up for adverse events and serious adverse events for 30 days following the last study dose.

